Over the counter lidocaine cream (5% concentration, for example: RectoCare®) is mixed in equal parts with Elefix electrolyte paste. This is done before each treatment session.

To calculate the amount of electrolyte/ lidocaine cream under one electrode, the space available under EGI's electrode cup is about 150 cubic mm. The total amount of paste under one cap is 150 mg. Half of this is an over-the-counter 5% lidocaine cream (and half is Elefix gel). The total amount of lidocaine is therefore 3.75 mg. If we assume 10 high current electrodes are treated, then if all were absorbed, the dose would be 10 times smaller than the systemic toxic threshold for a average patient weight of 70 kg (5mg /kg x 70 = 370 mg). Of course , the amount absorbed is a fraction of what is present at the skin. For example, lidocaine patches, even after 12 hours on the skin, still contain about 95 % of initial amount of drug and are recommended to be disposed with appropriate care.

Risk of Tissue Damage in Normal Operation

Tissue damage must be considered separately from pain. Pain is noticeable with changes in current density, including the offset of the current, apparently through stimulating scalp nerves. Furthermore, pain decreases to become unnoticeable with constant direct current (DC) in the typical tDCS paradigm. Tissue damage, however, is a function of current density over time, or charge density. Estimations of both safe and painless operation with conventional (large square sponges) tDCS (Bikson et al., 2009) have suggested that safe charge densities in the typical tDCS experiments with large wet sponge electrodes range from 343-960 C / m² (.0343-.0960 C / cm²). Nonetheless, there are reports of skin lesions when hard tap water (containing calcium carbonate) was used instead of saline (Palm et al., 2014). Furthermore, there have been reports

of skin lesions at the corners of large sponge electrodes, even though the estimation of charge density over the surface area of the electrode is lower than the safety limit (Rodriguez, Opisso, Pascual-Leone, & Soler, 2014). As shown in by the FEM simulation in **Figure 8**, the charge density is unlikely to be distributed evenly over the surface of the electrode, but rather is concentrated at the perimeter (and particularly the corners of square electrodes).

In a study for epicranial tDCS stimulation in rats, Liebetanz and colleagues report that brain lesions were observed at a minimum cathodal electrode current density of 142.9 A/m² for durations greater than 10 min (Liebetanz, Koch et al. 2009). For current densities between 142.9 and 285.7 A/m², lesion size increased linearly with charge density (current density × time); with an extrapolated zero lesion size intercept of 52400 C/m².

Mitigating the Risk of Tissue Damage in Normal Operation

In normal operation, the total current of the GTEN 100 is limited to 2 mA, and the electrode-scalp impedances are measured continually to assure that each electrode (for example 10 cathodes and many anodes) is maintained at or less than a current level of 200 μA (current density of 200 μA/cm²).

In the pulsed GTEN protocol, over 0.1 seconds (for example, a single pulse injected over 10 channels) in normal operation, the total charge density per electrode would be $0.0002 \text{ A/cm}^2 \times 1 \text{ C/(A} \times \text{s)} \times 0.1 \text{ seconds} = 0.00002 \text{ C/cm}^2$ (i.e. 0.2 C/m²) at the source electrode. Over the full pulsed GTEN session protocol of 3 pulse trains of 500 pulses of 0.1 second duration each, the total charge density would be $0.0002 \text{ A/cm}^2 \times 1 \text{ C/(A} \times \text{s)} \times (1500 \times 0.1) \text{ seconds} = 0.03 \text{ C/cm}^2$ (i.e. 300 C/m²) at the source electrode.

Tissue damage has been detected at a minimum total charge of 216 C/cm² (2,160,000 C/m²) (Yuen, Agnew et al. 1981). The normal GTEN 100 current flow at the source electrode is .001 (.204/216) of that limit. We have never seen skin damage, or any effects other than temporary reddening of the skin (erythemia) with the GTEN protocols and the Geodesic Sensor Net electrodes, even when current density varies from 200 to 400 μA over many minutes.

We also consider the risk of tissue damage in the brain. In a study for epicranial tDCS stimulation in rats, (Liebetanz, Koch et al. 2009), Liebetanz and colleagues report that brain lesions were observed at a minimum cathodal electrode current density of 142.9 A/m² for durations greater than 10 min. For current densities between 142.9 and 285.7 A/m², lesion size increased linearly with charge density (current density × time); with an extrapolated zero lesion size intercept of 52400 C/m².

Figure 8 shows an attenuation factor of about 20 X from the current level for multiple scalp electrodes (each at about 4 A/m²) to the cortical surface (peaking at about 0.2 A/m²). A similar calculation from one electrode (the worst case failure situation under less than astronomical odds for creating charge density of 2040 C/m²) shows an attenuation of about 100 X, from about 20 A/m² at the scalp to achieve 0.2A/m² on the cortex. With the attenuation of scalp charge density (2040 C/m²) by head tissues ranging from a factor of 80 to 120, the GTEN 100

normal mode charge density at the brain ranges from 26 C/m² to 17 C/m² or a factor of .0005 (26/52400) to .0003 (17/52400) of the safe limit for current to the brain.

The FDA reviewer cited earlier studies suggesting that the attenuation may be a factor of 30 rather than 100. Our modeling, with accurate skull conductivity from CT and with validation through bEIT studies, provides more accurate justification for the values than these early literature values. Nonetheless, we agree with the FDA that caution is warranted in assuming attenuation. As a result, we propose to mitigate the worst case failure through an additional layer of fault protection circuitry.

Note that (although it was not clearly explained in the previous submission), the GTEN 100 includes circuitry to limit the current per channel to 200 μ A. The fault protection is designed to limit total current assuming this circuit fails.

The GTEN 100 design has now been revised to include a second Sentinel Circuit®, in series with the first one, to insure that failure requires a triple fault (the circuit fault, and failure of both Sentinel Circuits). The Sentinel Circuit is a separate electronic monitor circuit that detects if the current level exceeds the planned 2 mA value (such as if there is a fault in the electronics circuit). In that event, the Sentinel Circuit disconnects the current generator.

Risk of Seizures in Normal Operation

An important risk of the GTEN treatment is the risk of causing seizures. This risk may not be simply related to the level of current, but rather involves the more complex and poorly understood neurophysiology of epilepsy. The evidence on treating epilepsy with both tDCS and rTMS is relevant to assessing the risk of seizures.

Mitigating the Risk of Seizures in Normal Operation

It should be emphasized that patients must agree to maintain their regular anti epileptic medication during the course of the study.

There are two studies we found that have examined the effects of a single session of tDCS treatment of the apparent epileptogenic zone (F. Fregni, Thome-Souza, et al., 2006; Rotenberg et al., 2008). Both showed beneficial short term effects of the treatment in suppressing epileptiform discharges, with no increase in seizure frequency.

For the pulsed GTEN protocol emulating the effects of slow rTMS, the literature on seizure risk with slow rTMS in epilepsy is relevant. An important caution is that there have been only a few studies of slow rTMS therapy in epilepsy. Nonetheless, a recent review of the literature for rTMS therapy suggests that there appears to be minimal risk of inducing seizures by the slow rTMS treatment (Bae et al., 2007). The seizures that have been recorded during the slow rTMS treatment session have been the patient's typical seizures in both duration and semiology, suggesting these were not induced by the treatment (Rotenberg et al., 2009).

Thus, for the present feasibility study, the literature suggests the risk of seizures is low. To mitigate the risk, we will monitor carefully for seizures during and after the treatment. During

the three-month pretreatment baseline evaluations, we will characterize the patient's interictal events, plus any ictal events that are recorded, during three two-hour dEEG evaluations. We will train the treatment technician to monitor the EEG for these events during the treatment session. Because the source site of the interictal events is also the presumed epileptogenic zone and the target of the GTEN treatment, this is also the site (and scalp topography) that would be expected to generate seizures if the treatment causes or kindles seizures. The preparation for each patient's treatment will identify not only the source of the epileptiform discharges, but the scalp topography, such that the technician has a select montage (screen arrangement) for the channels that reflect the patient's spikes (and likely seizures).

During the 17 minute GTEN treatment intervals, the EEG channels that are not used for (source or sink) current delivery will be monitored. The 24 bit ADs of the NA 400 allow adequate dynamic range (± 200 mV) that even channels nearby the current delivery seldom clip. During the rest (resting EEG and break) intervals, all 256 channels will be monitored. For the first ten patients, we will monitor the EEG for three hours following the completion of the treatment; for the rest of the patients we will monitor the EEG for 30 minutes following the completion of treatment.

If there is any increase in epileptiform activity during the treatment or the monitoring interval, interictal or ictal, the consulting epileptologist will review the EEG, the baseline EEGs, and the patient's history to decide if treatment should be discontinued. The patient and if relevant the family will be consulted in this decision.

Risk of Inducing Kindling of Seizures

It is well known that repeated electrical stimulation of the normal mammalian brain may lead to augmenting or progressive kindling of discharges, leading to seizures. Persons with epilepsy may show enhanced cortical excitability that places them at increased risk. In the animal literature, kindling occurs when repeated electrical stimulation of the cortex elicits cortical after-discharges (continuing when the stimulation stops); in some reports the discharges not only lead to seizures, but may lead to epilepsy, with spontaneous discharges and/or seizures in the absence of stimulation (Bertram, 2007).

Mitigating the Risk of Inducing Kindling of Seizures

The same procedures of careful EEG monitoring used to mitigate the risk of seizures will mitigate the risk of kindling. Specifically, the EEG of each patient will be monitored during and after the treatment session, including a specific inspection of the channels near the target site. If the GTEN treatment is observed to lead to any epileptiform discharges that are unlike the patient's typical discharges (spikes) in frequency or localization, the treatment will be discontinued. A specific warning for possible kindling is the observation of repeated discharges that are associated with the repeated application of stimulation, specifically the pulses of the pulsed GTEN protocol. If these are observed, treatment will be stopped.

Risk of Unwanted Plasticity

The short term effects of transcranial neuromodulation are typically assumed to be mediated by increasing or decreasing of cortical excitability. The longer term effects appear to reflect stable changes in cortical plasticity, including long term potentiation (LTP) and long term depression (LTD) as evidenced by learning effects that are mediated by NMDA (Monte-Silva et al., 2013). The rationale of the present interventions is that inducing long term depression in the epileptogenic zone will be effective in suppressing seizures. However, the scientific understanding of this manipulation is limited, such that there is risk of changing plasticity in ways that are unwanted or maladaptive.

Mitigating the Risk of Unwanted Plasticity

In addition to manipulating epileptiform activity, the GTEN treatment may change other aspects of the patient's cortical function that may create unwanted changes in brain function or plasticity. The large general literatures for tDCS and slow rTMS suggest there are unlikely to be serious unwanted changes. Nonetheless, we will achieve more focal and potentially more effective current delivery than in previous research with tDCS, and we will achieve deeper current delivery than previous research with slow rTMS.

The primary effect on the target brain region is expected to be the induction of long term depression. We will evaluate general cognitive function in each patient with scores on the California Verbal Learning Test, paying close attention to any changes from the expected improvement in performance with practice from the normative data. The patient's baseline performance with the CVLT is assessed during the pre-treatment baseline assessment. We will also review the Quality Of Life In Epilepsy ratings and the seizure diary with each patient and family, systematically reviewing any complaints or reports that may suggest the treatment is creating unwanted changes in brain function. Finally, for each patient we will examine the effective dose delivered to non target brain regions as a function of the DCSV targeting recorded by the GTEN Planning Module to insure that the electrical dosage (and the presumed induction of long term depression) is appropriately limited to the target cortex.

Pre-Clinical Testing with Normal Volunteers

We have studied the comfort and safety of the GTEN protocols, and evaluated their efficacy in manipulating cortical excitability, with normal volunteers. A preliminary report was presented at the June 2014 Organization for Human Brain Mapping ([name], Turovets, Anderson, & [name], 2014). In the first series of experiments, we limited the GTEN current delivery to 1 mA total, and applied this through 7 to 10 of the electrodes of the Geodesic Sensor Net for the anodal current and 7 to 10 electrodes for the cathodal current. Both saline and gel (Elefix) electrolytes were used. Typical tDCS protocols were evaluated, with head surface anodal current predicted to increase cortical excitability, and head surface cathodal current predicted to decrease cortical excitability (T. Wagner et al., 2007). Using typical tDCS procedures including ramping up the DC stimulation over several seconds, the 1 mA current levels were generally comfortable for the subjects, when distributed over 7 to 10 electrodes. The motor cortex was identified anatomically by the hand knob, and a typical tDCS targeting of the motor cortex was achieved with the GTEN Planning Module. The effect on cortical excitability was tested through TMS stimulation of the hand area to create a thumb Motor Evoked Potential (MEP), with the TMS strength (% of

initial motor threshold) defining cortical excitability. **Figure 9** shows the TMS and GTEN targeting.

[figure not shown]

Figure 9. Left: targeting of Motor Evoked Potential (MEP) with TMS (the red bulls eye is the TMS target). The cortex is rendered with a convex hull slice. Middle: GTEN source (red = anodal) and sink (blue = cathodal) pattern for a radial current flow pattern targeting the hand knob of motor cortex. Right: inflated brain to show sulcal current delivery.

Consistent with the tDCS literature, head surface anodal current generally increased cortical excitability as indexed by the TMS MEP, and head surface cathodal current generally decreased cortical excitability. Also consistent with the literature, individual responses varied considerably.

In the next series of experiments (now in preparation for publication), we tested the comfort level with higher current levels (200 μA for each 1 cm^2 electrode), using the typical tDCS protocol. Iontophoretic impedance conditioning was used to lower typical electrode-scalp impedances to 20 to 40K Ohms. There were large individual differences with comfort as well, but with the Geodesic Sensor Net 1 cm^2 electrodes and 7 to 10 with the primary cathodal or anodal current, most subjects reported minimal or no sensation at 50 μA , feelings of itching or minor pain at 100 μA , and noticeable itching and painful irritation at 200 μA . We then mixed lidocaine with the gel electrolyte, applied anodal current for iontophoretic delivery (see above for dose analysis) during the iontophoretic impedance conditioning, and then repeated the experiments at 200 μA . Subjects consistently reported this was a painless procedure. Only when we asked them to feel the scalp with their fingers did they notice the slight numbing of the scalp under the active (7 to 10 focal anodal or cathodal) electrodes.

We have now completed testing with normal volunteers with the Pulsed GTEN protocol. Initial tests (with the investigators) without lidocaine confirm that the pulsed stimulation is more painful than ramped and sustained tDCS, even at 100 μA . However, with the lidocaine iontophoresis, the 200 μA per electrode results in no noticeable sensation with the pulsed protocol. These pulsed experiments will be completed and submitted for publication, with the requirement that safety and comfort are both verified with normal volunteers prior to initiating clinical feasibility trials with the Pulsed GTEN protocol.

Therapeutic Mode of Action

In addition to insuring safety, we want to suppress seizures effectively. The literature on electrical neuromodulation in epilepsy suggests that tDCS typically has only a short term therapeutic effect in suppressing epileptiform discharges or EDs (Auvichayapat et al., 2013; Faria, Fregni, Sebastiao, Dias, & Leal, 2012). However, other evidence (Monte-Silva et al., 2013; Monte-Silva, Kuo, Liebetanz, Paulus, & Nitsche, 2010) suggests that repeated blocks of tDCS can induce lasting changes in cortical excitability (even though these studies were not with epilepsy).

In addition, the literature on epilepsy treatment suggests that slow (1 Hz or 0.5 Hz) repetitive transcranial magnetic stimulation (slow rTMS) has a lasting effect, including seizure suppression, assuming that the epileptogenic zone is accurately targeted (F. Fregni, Otachi, et al., 2006; Sun et al., 2012). Considering these several lines of evidence, we propose to implement a Pulsed TEN protocol to emulate the brain currents induced by slow rTMS to induce LTD and decrease cortical excitability.

Both tDCS and TMS achieve neurophysiological effects through creating electrical currents in the brain. Whereas the induction of current by the magnetic field of the TMS coil has the advantage of delivering higher brain currents while minimizing painful current flow through the scalp, the current flow is almost exclusively tangential to the head surface (because of the mechanical constraints of the coil), and the current is limited to roughly two centimeters of depth from the head surface, depending on the coil design (Pascual-Leone, Davey, Rothwell, Wassermann, & Puri, 2002)). As a result, even if the epileptogenic zone is localized correctly, effective targeting (current flow normal to the cortical surface) is difficult (and often impossible) with TMS. This conclusion is supported by the finding that TMS is often successful with neocortical foci, but may not be successful with deep medial temporal foci (F. Fregni, Otachi, et al., 2006; Sun et al., 2012).

The initial, single treatment session application of cathodal tDCS in epilepsy has suggested there is a suppression of epileptiform activity, but only over days or weeks (Auvichayapat et al., 2013; Faria et al., 2012). Our goal is suppression over several months. Several recent lines of evidence have suggest that the effects of tDCS stimulation can be made more lasting in two ways: (1) separating the repeated blocks of stimulation by short intervals of no stimulation, and (2) by repeating treatment over successive days.

In a cathodal tDCS study, Monte-Silva et al. (2010) showed that two, 9-minute tDCS sessions separated by brief (3 or 20 minute interval) breaks (i.e., no stimulation)

[figure not shown]

Figure 10. The protocol for interleaving GTEN treatment (either Blocked Sustained tDCS or Pulsed GTEN) and dEEG assessment (recorded and evaluated during the breaks as well as the resting EEG intervals).

enhanced the inhibitory after effect as well as prolonged it (up to two hours). They also showed that 9-minute sessions separated by 3 or 24 hours reduced the immediate aftereffects, but within 25 minutes after tDCS was completed the aftereffects were then enhanced and sustained for up to 2 hours. In a more recent study, Monte-Silva et al. (2013) showed that 13-minute anodal stimulation sessions separated by 3 or 20 minute intervals extended the aftereffects beyond 24 hours post-stimulation. From both studies, when tDCS is applied within the aftereffect window of the first tDCS session, it has the ability to enhance the lasting aftereffects (i.e., inhibit or facilitate neuronal function depending on cathodal vs anodal polarity) as well as to prolong these effects in time.

Two studies have found that tDCS applied over multiple days produces learning effects that last for weeks to several months. Reis et al. applied 20-minute anodal tDCS over five consecutive sessions (each separated by 24 hours) as subjects performed a visuomotor task (Reis et al., 2009). The effect of anodal tDCS on task performance was measured at five intervals, the longest interval being 85 days after tDCS. Reis et al. found that tDCS enhanced motor learning and that this enhancement persisted for up to 85 days post tDCS treatment. More recently, Olma et al. applied anodal tDCS to the visual cortex over five consecutive days (each separated by 24 hours) as subjects performed a visual motion perception task (Olma et al., 2013). Anodal tDCS in this paradigm resulted in an improvement in motion perception that lasted up to 28 days.

Of course these are not just direct neurophysiological effects of tDCS, but rather learning changes in the brain where the process of learning has been augmented by tDCS. Treating epilepsy may be more challenging because there is no systematic or deliberate learning regimen, but rather a more simple attempt to suppress cortical excitability.

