The dEEG is reviewed after each treatment and follow up session, by visual inspection by a trained electroencephalographer and with an automated spike detection and clustering algorithm (EGI's Spike Beacon software), with the quantitation reported as a trial endpoint. If there is an apparent change in the spike (and possibly seizure) localization, as indicated by the spike topography clustering, Electrical Source Imaging is conducted with GeoSource to determine if there is a change in localization. If there is a change in localization, or if there is an increase in spike frequency of over one standard deviation compared to the baseline sessions, or if there is non typical seizure activity, the results are conveyed to the epileptologist supervising the clinical trial to evaluate the risk for the patient's continuation of the trial.

The experimental procedures for each patient session are summarized in Table 2.

Monitoring of Risk

A daily diary with a count and description of seizures is reviewed at each session (treatment and follow up). If there is an increase in seizures of two-fold over the patient's baseline levels, the patient's treatment is suspended and the safety of the treatment is evaluated by the epileptologist, patient, and family. In the follow up sessions, routine dEEG evaluations, cognitive function assessments, and quality of life ratings are conducted once each week for three weeks following the treatment, and then week 8. At each follow up session, cognitive function is assessed with the California Verbal Learning Test, a widely used and easily administered test (www.pearsonclinical.com), and quality of life is assessed with the Quality of Life In Epilepsy Questionnaire (http://www.rand.org/health/surveys_tools/qolie.html).

Overview of Study Protocol

Table 2 presents an overview of the treatment protocol. An exception is that for the first ten patients the dEEG will be monitored for seizures for 3 hours after the first treatment session.

Session	Procedure
Pre-Treatment Evaluation	Review of seizure diary each week for one month. Two routine dEEG evaluations to capture epileptiform discharges (ED), including spikes and seizures. MRI when available to determine possible malformations of cortical development and build individual head model.

Session	Procedure

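### For non-typical seizures and for a two-fold seizure increase during the treatment week, the monitoring sections prescribe a weaker response than the stopping rules

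*Protocol*

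**What the plan says.** All places are in the Protocol.

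**Non-typical seizures.** *Study Monitoring Committee* classes seizures that are not typical of the patient as treatment-induced and requires that treatment be discontinued. *Review of the EEG for Safety and for Spike Counts* covers the treatment week, since "The dEEG is reviewed after each treatment and follow up session". Its response to the same event is: "or if there is non typical seizure activity, the results are conveyed to the epileptologist supervising the clinical trial", for a judgment on whether the patient should continue.

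**Two-fold seizure increase.** Escape criterion 5 ends the study for the individual patient, and *Study Monitoring Committee* counts a doubling over baseline as treatment-induced and discontinues treatment. *Monitoring of Risk*, which applies at every treatment and follow-up session, says the patient's "treatment is suspended and the safety of the treatment is evaluated by the epileptologist, patient, and family". Criterion 5 has an exception for patients with very few seizures: an apparent increase that cannot be reliably quantified as two-fold is discussed with patient, family, physician and committee.

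**Spike location and frequency.** The stop in *Mitigating the Risk of Inducing Kindling of Seizures* is conditional on cause: "If the GTEN treatment is observed to lead to any epileptiform discharges that are unlike" what is usual for that person. The sentence then closes with the standard of comparison and the consequence: "typical discharges (spikes) in frequency or localization, the treatment will be discontinued". For discharges that follow the pulses repeatedly it adds: "If these are observed, treatment will be stopped". *Mitigating the Risk of Seizures in Normal Operation* has the epileptologist review any increase in epileptiform activity against the baseline EEGs and the patient's "history to decide if treatment should be discontinued". *Review of the EEG for Safety and for Spike Counts* uses the same referral route: "If there is a change in localization, or if there is an increase in spike frequency of over one standard deviation" relative to baseline, the epileptologist is told and evaluates the risk.

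**The concern.** *Risks of GTEN Treatment and Mitigation of Risks* names worsening seizures and induced discharges, possibly leading to kindling, as the significant risk behind the IDE request. The stopping and monitoring rules are the mitigation offered for that risk, so they should give one answer to one event.

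For the two seizure events they give two. Someone working from the EEG review section could treat continuation after a non-typical seizure as an open question, although *Study Monitoring Committee* has already settled it. Someone working from *Monitoring of Risk* could resume stimulation after a confirmed doubling of seizures, although the escape criteria do not allow that.

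The second case also bears on the trial as a whole. The study ends when five subjects meet escape criteria. If a doubling is handled as a suspension and later resumed, the text does not say whether that patient has met a criterion.

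**Working it through.** The protocol states no figure for this point, so the check is mainly a comparison of texts. The arithmetic only sizes what is at stake.

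**1. Do the rules overlap in time?** Yes. The EEG review follows each treatment session as well as each follow-up session, and the diary is reviewed at both kinds of session.

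**2. Side by side**

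| Event in the treatment week | Firm text | Softer text | Reconciled in the text? |
|---|---|---|---|
| Non-typical seizure | Discontinue (*Study Monitoring Committee*) | Refer, evaluate continuation (*Review of the EEG*) | No |
| Two-fold seizure increase, reliably quantified | End study for the patient (*Escape Criteria*); discontinue (*Study Monitoring Committee*) | Suspend, then evaluate (*Monitoring of Risk*) | No; the low-frequency exception covers only unreliable doublings |
| New spike location, or changed spike frequency | Discontinue if treatment led to it (*Kindling*) | Refer (*Risk of Seizures*; *Review of the EEG*) | Possible as two tiers, but not stated |
| Pulse-linked discharges | Stop (*Kindling*) | None | No conflict |

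The first row assumes that non-typical seizure activity on the dEEG is a seizure that is not typical of the patient.

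**3. Stimulation at stake.** Table 2 gives 3 sets of 500 pulses per session, and *Therapeutic Mode of Action* gives five daily sessions.

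- Per session: 3 × 500 = 1,500 pulses. Course: 5 × 1,500 = 7,500.
- Event in session 1: 4 × 1,500 = 6,000 pulses remain, 6,000 / 7,500 = 80%.
- Event in session 4: 1,500 remain, 20%.
- At 0.5 Hz, 500 pulses take 1,000 s = 16.7 min, matching the 17-minute block. So 6,000 pulses take 12,000 s = 200 min.

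These are upper bounds. They are reached only if the epileptologist lets treatment continue after a non-typical seizure, or if treatment suspended for a doubling is resumed with no sessions lost.

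**4. For whom is a doubling reliably quantified?** Entry requires two or more seizures in the last month. At 2 per month, 2 × 5/30 = 0.33 are expected in five days and a doubling is 0.67, so one seizure already exceeds it. At 30 per month, 5 are expected and a doubling is 10.

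As an illustration, take Poisson counts, no true change, one baseline month of 4.345 weeks and at least one baseline seizure. The probability that one week's count reaches twice the baseline weekly rate is:

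| Seizures per month | Probability |
|---|---|
| 2 | 0.26 |
| 4 | 0.25 |
| 8 | 0.16 |
| 30 | 0.03 |

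At low rates an apparent doubling is often chance, and criterion 5's exception is needed. The conflict matters for patients with frequent seizures.

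**5. Should a spike increase over one SD be a stop in itself?** Assume the SD comes from the two baseline dEEGs, rates are independent and normal, and there is no treatment effect. One session exceeds mean + 1 SD with probability P(t with 1 df > 1/√1.5) = 0.28. In simulation, at least one of five sessions does so with probability about 0.63. Under these assumptions the trigger is too common to serve as an automatic stop, which favours keeping it as a referral.

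**The case against.** The strongest reply is that the softer passages describe escalation, not a different rule. *Study Monitoring Committee* makes the site epileptologist responsible for each patient's safety decisions, and *Treatment Protocol* gives that person the decision to terminate treatment. Telling the epileptologist need not cancel a rule the epileptologist must then apply. This stands as a possible reading. However, the EEG review section presents continuation as the question to be evaluated, and *Monitoring of Risk* brings patient and family into an open evaluation. Neither says that the outcome is fixed elsewhere.

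A reader might infer more than the text supports in four ways:

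- **That spike location and frequency rules also contradict each other.** The kindling stop applies to discharges that treatment is observed to cause, while the referrals cover changes not yet attributed. Refer first, then stop on attribution, is a coherent reading. What remains is that the protocol does not state it and sets no boundary for frequency.
- **That stimulation simply carries on after a doubling.** It does not: *Monitoring of Risk* suspends it at once. Only resumption is open, and for patients with few seizures the exception in criterion 5 leads to nearly the same discussion.
- **That several sites will diverge.** Three are planned, but *Changes to the Harborview Informed Consent Form* names a single active site.
- **That stops must be reported to the committee by reason.** The committee already reviews safety across sites. A particular report format is a preference, and its absence is no contradiction.

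**Conclusion.** The point holds for two events. For non-typical seizures the difference is discontinuation against referral. For a reliably quantified two-fold increase it is termination against suspension with possible resumption, plus an unclear count toward the five-subject stop. No sentence sets an order of precedence. For spike location and frequency the finding is only that the two tiers are left unstated.

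The stake per affected patient runs from 20% of the course (event in session 4) to 80% (event in session 1), as upper bounds. The protocol gives no event rates, so how often the texts would lead to different actions cannot be computed. The probabilities in the working rest on assumed distributions and do not estimate that frequency. This should be fixed: it concerns the principal risk of the trial and takes little text.

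**What to change.** **In *Review of the EEG for Safety and for Spike Counts* and *Monitoring of Risk*, state that during the treatment week:**

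1. A non-typical seizure means treatment is discontinued, as *Study Monitoring Committee* requires.
2. A two-fold seizure increase, once confirmed, means discontinuation under *Escape Criteria* and *Study Monitoring Committee*. Suspension applies only until confirmation. The patient counts as an escape. The low-frequency exception in criterion 5 is unchanged.
3. A change in spike localization, or a spike increase of more than one SD, is reviewed by the epileptologist before the next session. Treatment is discontinued under the kindling section if the change is attributed to the stimulation.

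Item 3 should not become an automatic stop for every localization change, because that would be stricter than the kindling section.

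**Cost.** A few sentences. There would be a few more mandatory stops, so slightly fewer patients would complete all five sessions.
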